### 9.1 Analysis Data Sets

The primary analysis will be conducted on the Intent to Treatment (ITT) data set. The ITT data set will consist of all donations where randomization was completed and the apheresis procedure was started by "Begin Draw" on the NexSys® PCS device.

Sensitivity analysis may be conducted using a Modified *ITT* (MITT) data set and the per-protocol data set. The MITT data set will consist of all complete donations (see Section 6.1.2), as well as all donations associated with a significant hypotensive (vasovagal/hypovolemia) adverse event according to the plasma center adverse event reporting system, based on the IQPP definitions.

The per protocol data set will consist of all donations where the apheresis procedure was successfully completed collecting at least 90% of target plasma volume as well as all donations associated with a significant hypotensive (vasovagal/hypovolemia) adverse event according to the plasma center adverse event reporting system, based on the IQPP definitions.

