procedure. Their study group assignment will be changed to the administered procedure group and the donor will be expected to donate only in this study group.

• If the donor happens to donate in both study groups (Allocation Miss-Assignment happens after the first donation or it happens twice) the donor will be discontinued. The study group associated with the donor will follow the procedure that the donor administered at the first donation.

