2.2.2. STUDY POPULATIONS

The ITT data set will consist of all study donations were the apheresis procedure was started by "Begin Draw" on the NexSys® PCS device. The ITT population will include all Study Adverse Events.

The Modified Intent to Treat (MITT) data set is a subset of the ITT data set which consists of all complete study donations, as well as all donations associated with a moderate or severe adverse event [not just hypotensive (vasovagal/hypovolemia)] defined according to the IQPP and associated with the study donations. A donation is considered complete if the total plasma volume collected is at least 200 mL. A donation is considered incomplete if the total plasma volume collected is less than 200 mL.

The Per-Protocol (PP) data set will consist of all donations without major protocol deviations where the apheresis procedure is successfully completed collecting at least 90% of the target plasma volume, as well as all study donations associated with a moderate or severe adverse event [not just hypotensive (vasovagal/hypovolemia)] defined according to the IQPP.

Statistical Analysis Plan Version: 1.0 Date: 26-Apr-2020

The Extended AE Population (EAEP) is defined as consisting of ITT population with the addition of all the AEs that were reported as associated with Non-Study donations in donors previously enrolled in the study and reported within two calendar weeks post study last day.

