3. DATA ANALYSIS

3.1. PRIMARY ANALYSIS

Primary analysis will be conducted on ITT population. Sensitivity analysis will be conducted using MITT and PP populations. Additional sensitivity analysis may be conducted using EAEI population.

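### The per-protocol set drops deviating donations unless they had a moderate or severe AE, so it cannot remove events that followed a wrong-arm procedure

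*SAP*

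**What the plan says.** SAP 2.2.2 builds the PP set in two parts. The base is "all donations without major protocol deviations where the apheresis procedure is successfully completed collecting at least 90% of the target plasma volume". To this it adds donations with an event: "as well as all study donations associated with a moderate or severe adverse event", of any type and not only hypotensive. The MITT set is the part of ITT "which consists of all complete study donations, as well as all donations associated with a moderate or severe adverse event", where complete means at least 200 mL. MITT has no deviation criterion.

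Protocol 9.1 uses the same device more narrowly. Its two sets re-admit donations on the primary outcome only ("as well as all donations associated with a significant hypotensive (vasovagal/hypovolemia) adverse event"), and its PP set has no deviation criterion.

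SAP 1.2.3 treats Allocation Miss-Assignment as a protocol deviation but does not say whether it is major. If it happens at the first donation, the donor is relabelled: "Their study group assignment will be changed to the administered procedure group". If the donor donates in both groups, the donor is discontinued and "The study group associated with the donor will follow the procedure that the donor administered at the first donation".

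The primary analysis is on ITT. SAP 3.1 adds: "Sensitivity analysis will be conducted using MITT and PP populations".

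**The concern.** A donation that is short (PP and MITT) or has a major deviation (PP) leaves the set if it was event-free and stays if it had a moderate or severe AE. If all primary events count as moderate or severe, both sets keep the ITT numerator and only lose event-free donations from the denominator.

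This matters most for contamination, meaning a donation run with the other arm's procedure. In a non-inferiority trial contamination pulls the arms together, and a PP analysis is normally expected to show how much. Take a control donor who is given the experimental procedure at a later donation. If that donation is event-free and the deviation is major, it leaves PP. If it has a qualifying event, it stays in PP and counts as a control event. The sensitivity set then keeps exactly the donations that it should set aside.

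**Working it through.** **Inputs from the SAP.** Margin 0.0015 on the rate difference (3.1.2); one-sided 2.5%, event rate 0.0015, 24,000 donations and 3,000 donors per group (section 5); 1:1 allocation (1.2.3), so 12,000 donations per arm and 12,000 × 0.0015 = 18 expected events.

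**Assumptions.** Exclusion and contamination shares (the documents give none); donations treated as independent; every primary event counts as moderate or severe; miss-assignment counts as a major deviation.

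**The plan's own figure.** With both rates at 0.0015, SE = √(2 × 0.0015 × 0.9985 / 12,000) = 0.0004996. Power = Φ(0.0015/0.0004996 − 1.96) = 85.1%, which agrees with the stated power above 85% (85.0% by simulation).

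**Step 1: short donations.** If a share d of event-free donations is excluded, an arm's rate becomes p / [p + (1 − p)(1 − d)].
- Equal shares: a true difference of 0.0015 (0.0030 v 0.0015) becomes 0.00158 at d = 5% and 0.00187 at d = 20%. With no true difference, the simulated chance of showing non-inferiority falls from 85.0% to 81.5% and 67.9%. This is conservative.
- Unequal shares, both true rates 0.0015: d = 10% gives 0.0015/0.90015 = 0.001666; d = 5% gives 0.0015/0.950075 = 0.001579. The difference is 0.000088, or 0.009 percentage points and 6% of the margin. It goes against non-inferiority if the experimental arm loses 10%, and towards it if the control arm does.
- Unequal shares are plausible because the 90% rule is measured against arm-specific targets: 28.5% of plasma volume up to 1,000 mL (Protocol 2.1) against weight bands up to 800 mL (Protocol 1.4, Table 1).

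**Step 2: crossover donations.** True rates are 0.0015 control and 0.0030 experimental, so the true difference is 0.0015. Suppose 5% of control donations (600) receive the experimental procedure.
- Control events: 11,400 × 0.0015 + 600 × 0.0030 = 17.1 + 1.8 = 18.9.
- ITT: 0.0030 − 18.9/12,000 = 0.0030 − 0.001575 = 0.001425 (simulated mean 0.001424, hence 0.00142).
- PP as defined: the 598.2 event-free crossovers leave and the 1.8 with events stay. 0.0030 − 18.9/11,401.8 = 0.0030 − 0.001658 = 0.001342.
- Outcome-blind PP: 0.0030 − 17.1/11,400 = 0.001500.

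The simulated chance of wrongly declaring non-inferiority is 3.8% (ITT), 4.8% (PP as defined) and 2.8% (outcome-blind PP).

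The same formulas for other patterns:

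| Assumed contamination | ITT | PP as defined | Outcome-blind PP |
|---|---|---|---|
| 1% of control | 0.001485 | 0.001470 | 0.001500 |
| 5% of control | 0.001425 | 0.001342 | 0.001500 |
| 10% of control | 0.001350 | 0.001167 | 0.001500 |
| 5% of each arm | 0.001350 | 0.001421 | 0.001500 |
| 5% of experimental | 0.001425 | 0.001579 | 0.001500 |

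With 5% in each arm, PP recovers (0.001421 − 0.001350)/(0.001500 − 0.001350) = 47% of the dilution. With experimental-only contamination it overshoots. In none of these patterns does it return the uncontaminated difference.

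**Step 3: how likely.** A donor who donates in both groups is discontinued. At one crossover per donor, 600 crossovers would mean 600/3,000 = 20% of control donors, and 1% (120 donations) would mean 4%. At 1%, the expected events are 120 × 0.0015 to 0.0030 = 0.18 to 0.36, and PP and ITT differ by 0.000015, about 1% of the margin.

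**The case against.** The add-back has a sound motive. A hypotensive event can itself end a donation below 200 mL or below 90% of target, and a volume rule alone would delete safety events. That stands for short donations. It does not extend to deviating donations, since an AE does not cause a miss-assignment.

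Contamination is also limited elsewhere. PPN is disabled by default on control devices (Protocol 3.2), the arms' devices stand apart and each subject is verified (Protocol 8.3), and assigned versus actual randomization is monitored and analysed (Protocol 9.8, SAP 3.3). This stands, and it is why the effect is probably small. Protocol section 9 also lets the SAP modify the protocol's plans, so the difference between the two PP definitions is not in itself a breach.

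A reader might infer four stronger things that the documents do not support:
- That PP is blind to contamination. If miss-assignment is major, event-free crossovers do leave. With 5% in each arm, PP is nearer the truth than ITT (simulated false declaration 3.8% v 4.9%).
- That MITT also drops deviating donations. It excludes on volume alone.
- That any AE re-admits a donation. It must be moderate or severe.
- That the definitions favour non-inferiority. Equal exclusion works against it, and unequal exclusion can go either way.

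**Conclusion.** The point holds as a defect in a planned sensitivity analysis of the primary endpoint. Inclusion in PP and MITT depends on the outcome, and PP cannot remove contaminated events. Under assumed 5% control-only contamination, PP is less protective than the ITT result that it should test (0.00134 v 0.00142, against 0.00150). At 1% the gap between PP and ITT is about 1% of the margin. The ITT primary result and the non-inferiority decision are unaffected.

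The sizes rest on the assumed shares and on miss-assignment being a major deviation. If it is not major, crossover donations do not leave PP on that ground at all, and the set still does not remove them. They also assume that the add-back covers every primary event. The table in Protocol 5.1 gives the loss-of-consciousness rows 1.3 and 1.4 no moderate or severe label, so this too should be stated.

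**What to change.** For the AE sensitivity analysis:
- Define PP as ITT donations without major deviations.
- Define a major deviation, and state that Allocation Miss-Assignment is one (or analyse those donations by procedure received).
- Do not re-admit a deviating donation because it had an AE.
- Apply no volume criterion. Donations cut short by an AE then stay in without an add-back.

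Keep the 200 mL and 90% sets for the plasma-volume analyses, and align Protocol 9.1 with the SAP.

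The cost is wording in two documents. The sensitivity estimate will be slightly less precise, and the few AEs in deviating donations will appear only in ITT.

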3. DATA ANALYSIS

3.1. PRIMARY ANALYSIS

Primary analysis will be conducted on ITT population. Sensitivity analysis will be conducted using MITT and PP populations. Additional sensitivity analysis may be conducted using EAEI population.

3.1.1. STATISTICAL ANALYSIS METHOD

Given the nature of the data where donors contribute multiple data samples (donations), Generalized Estimation Equations Logistic Regression (GEE Logistic) framework for the repeat measures will be used (Halekoh, 2006; Yan J, 2004). The regression equation is presented below with Patient ID representing the random effect, and plasmapheresis method (study group) being fixed effect. Additional covariates are age, gender, BMI, and first-time donor status.

 $Logit(P(AE_{i,t}=1)) = \beta_0 + \beta_{Treatment} \times Treatment_i + \beta_{Age} \times Age_{i,t} + \beta_{Gender} \times Gender_i + \beta_{First \ Comer} \times First \ comer_{i,t} + \beta_{BMI} \times BMI_{i,t} + \varepsilon_{i,t},$

Corr(AE_{i,j}, AE_{i,k}) is exchangeable across all donors.

$$Corr(AE) = \begin{bmatrix} 1 & \gamma & \gamma & \gamma \\ \gamma & 1 & \gamma & \gamma \\ \gamma & \gamma & 1 & \gamma \\ \gamma & \gamma & \gamma & 1 \end{bmatrix}$$

Statistical Analysis Plan Version: 1.0 Date: 26-Apr-2020

AE represents the occurrence of a hypotensive AE (at least one), during the plasmapheresis procedure. *Treatment* is the variable representing plasmapheresis group (1=Experimental group, 0=Control group). For the *Gender* variable 1=Female, 0=Male. In *First comer* variable 1=First-time donor and 0=Repeat donor. First-time donors are those who have never undergone a plasmapheresis procedure. Age and BMI are continuous variables. i represents subject ID and t represents donation number for the given i subject.

Correlation structure within patients will be assumed to be exchangeable. Derivation of the final correlation model is currently in progress. The correlation structure can also be defined with the use of the historic data from the current study centers.

The above modeling will be used to obtain estimates of difference in proportions of significant hypotensive (vasovagal/hypovolemia) AE rates ($P_{Exper} - P_{Ctrl}$) in experimental and control groups along with its one-sided 97.5% upper limit of the CI calculated with Wald method.

[figure not shown]

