# 2.4 Expected Impact on Hypotensive (Vasovagal / Hypovolemia) Reactions

Hypotensive (vasovagal/hypovolemia) donor adverse events according to the plasma center adverse event reporting system, based on the IQPP definitions, are influenced by the extracorporeal volume (ECV) during the procedure and the intravascular deficit (IVD) at the end of the procedure.

During the procedure, the peak ECV on the NexSys® PCS is reached when the full plasma product has been collected and the separation chamber contents are about to be returned to the donor for the last time. Since the PPN feature modifies the target plasma collection volume, it has an impact on peak ECV. Peak ECV will go down for donors whose target plasma collection volume is decreased and up for donors whose target is increased.

The range of peak ECV using the current FDA nomogram with YES® Technology is 12.2 % to 30.3%, with a median of 19.3% and a mean of 19.1%, in the database of donor biometric information from 111,916 plasmapheresis procedures (see above). This range is created by factors such as target plasma collection volume and donor plasma and blood volume. The use of the PPN feature would tighten the distribution since the target plasma collection volume would be personalized to the donors' total plasma volume, with a hypothetical range of 14.4% to 24.6%, a median of 20.3%, and a mean of 20.2%. The results of this analysis are shown in Figure 5 below.

[figure not shown]

Figure 5 – Peak Extracorporeal Volume with existing nomogram and PPN

On the left, "Existing Nomogram" represents the ECV challenge that is experienced in the field today and that will be experienced in the clinical trial in all 'Control' procedures. On the right, "Proposed Nomogram" is the challenge predicted for the 'Experimental' procedures that will use the PPN feature in the trial.

The donors considered to be most at risk for significant hypotensive (vasovagal/hypovolemia) adverse events would be those in the upper quartile of the distribution. To assess the risk in the clinical trial, we analyzed this quartile of the donors in both the 'Control' and the 'Experimental' distributions.

We conclude that the donors in the 'Experimental' arm are not expected to have an increased risk of ECV-induced significant hypotensive (vasovagal/hypovolemia) adverse events compared to the 'Control' donors for the following reasons:

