## 5.1 Primary Endpoint

The primary endpoint of the clinical trial is the incidence rate of at least one significant hypotensive (vasovagal/hypovolemia) adverse event according to the plasma center adverse event reporting system, based on the IQPP definitions below.

For the purpose of this clinical trial, a hypotensive (vasovagal/hypovolemia) adverse event will be determined to be *significant* if it fulfills one or more of the criteria defined in rows 1.2 (Hypotensive: Prefaint, No LOC (moderate)) or 1.3 (Hypotensive: LOC (brief)) or 1.4 (Hypotensive: LOC (prolonged)) or 1.5 (Hypotensive; Severe (With or Without LOC)) or 1.6 (Hypotensive; Injury) of the IQPP definition, as applied in the plasma center adverse event reporting system. The table below is an excerpt from the current IQPP adverse event classification criteria. See Appendix 16.1 IQPP Standard for Recording Donor Adverse Events.

The signs/symptoms/findings for categories 1.1. to 1.6 that are listed in the far right column of the table may be defined slightly differently per center policy. For example, Octapharma Plasma uses a symptom-based approach for adverse event classification that entails at least two layers of internal review. Event categorization as a hypotensive (vasovagal/hypovolemia) adverse event is always confirmed by a physician per Octapharma Plasma policy. Per current policy, the following criteria are considered indicative of convulsions/seizures that are listed under criterion 1.5, last column on the right, in the table above: a. Bluish tinge to skin, lips (cyanosis) b. Breath-holding c. Curling of fingers/toes d. Drooling e. Muscle twitching f. Tongue biting. Any checkmark applied to one of these categories will be considered indicative of the convulsions/seizure criterion. The criterion "Nausea" under criterion 1.1 in the last column on the right of the IQPP criteria is not listed as a separate criterion in Octapharma Plasma's Medical Incidence Report (MIR) system. As systolic blood pressure is determined and recorded under vital signs in each MIR and at least two reviews of the classification of an adverse event as hypotensive (vasovagal/hypovolemia) are required per Octapharma Plasma policy, a separate checkbox for the category "Hypotension", as under 1.1 under the IQPP criteria, is not required on the MIR.

DAE Classification	Description	Signs/Symptoms/Findings	

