1. INTRODUCTION

1.1. STUDY OBJECTIVES

1.1.1. PRIMARY OBJECTIVE

The primary objective of the IMPACT clinical trial is to evaluate the safety of plasmapheresis performed on the NexSys® PCS device with Percent Plasma Nomogram (PPN) feature. The clinical trial is designed to assess if the incidence rate of significant hypotensive (vasovagal/hypovolemia) adverse events per donation in donors undergoing plasmapheresis in the experimental group is NOT inferior to that seen in donors in the control group. This incidence rate is defined as at least one (1) significant hypotensive (vasovagal/hypovolemia) adverse event according to the plasma center adverse event reporting system, based on the IQPP definitions, per plasmapheresis procedure (See Appendix 1 IQPP Standard for Recording Donor Adverse Events). For the purpose of this clinical trial, a hypotensive (vasovagal/hypovolemia) adverse event will be determined to be significant if it fulfills one or more of the criteria defined in rows 1.2 (Hypotensive: Prefaint, No LOC (moderate)) or 1.3 (Hypotensive: LOC (brief)) or 1.4 (Hypotensive: LOC (prolonged)) or 1.5 (Hypotensive; Severe (With or Without LOC)) or 1.6 (Hypotensive; Injury) of the IQPP definition, as applied in the plasma center adverse event reporting system. See Appendix 1 IQPP Standard for Recording Donor Adverse Events. The signs/symptoms/findings for categories 1.1. to 1.6 that are listed in the far right column of the table may be defined slightly differently per center policy.

ClinStatDevice

Statistical Analysis Plan Version: 1.0 Date: 26-Apr-2020

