2.2. DEFINITIONS OF ANALYSIS DATA SETS

2.2.1. DEFINITIONS

Study Donor is defined as a study participant who consented to the study and was randomized to a study procedure (control or experimental).

Statistical Analysis Plan Version: 1.0 Date: 26-Apr-2020

Study Donation is defined as a donation that took place during the course of the study and is associated with the study donor.

Non-Study Donation is defined as a donation that took place either before the study start date or after the last date of the study.

Study Adverse Event is defined as an adverse event that was reported to be associated with the study donation.

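### SAP 3.1.1 defines the primary model's outcome without 'significant' and only during the procedure, in conflict with its own estimand, the primary endpoint and the SAP's adverse event definitions

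*SAP*

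**What the plan says.** SAP 3.1.1 gives the regression equation and then explains its dependent variable: "AE represents the occurrence of a hypotensive AE (at least one), during the plasmapheresis procedure". The last paragraph of that section describes the output of the same model differently: "The above modeling will be used to obtain estimates of difference in proportions of significant hypotensive (vasovagal/hypovolemia) AE rates".

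The other relevant places are:

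- **Protocol 5.1:** "The primary endpoint of the clinical trial is the incidence rate of at least one significant hypotensive (vasovagal/hypovolemia) adverse event". Significant means rows 1.2 to 1.6 of the IQPP table, so row 1.1 (minor prefaint) does not count. No time window is given.
- **SAP 1.1.1:** "This incidence rate is defined as at least one (1) significant hypotensive (vasovagal/hypovolemia) adverse event according to the plasma center adverse event reporting system". The rate is counted per procedure, which sets the unit of analysis rather than a time window.
- **SAP 2.2.1:** "Study Adverse Event is defined as an adverse event that was reported to be associated with the study donation".
- **SAP 2.2.2:** "The ITT population will include all Study Adverse Events". The ITT set is the primary analysis set.
- **SAP 3.3:** row 1.1 events have their own exploratory estimates by arm.

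**The concern.** The sentence in 3.1.1 is the SAP's only definition of the variable that enters the confirmatory model, so it is what a programmer would code. It departs from the endpoint in two ways.

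- **Event class.** Without the word *significant*, row 1.1 events qualify. The trial was sized on a rate for significant events, so adding minor events raises the variance against a fixed absolute margin and costs power.
- **Timing.** A faint after disconnection counts under SAP 2.2.1 and 2.2.2 but not under 3.1.1. In a safety non-inferiority trial, dropping events shrinks the observed difference towards zero, which favours the experimental arm if it is harmful. Protocol 2.4 names "the intravascular deficit (IVD) at the end of the procedure" as one of two influences on these reactions, so the period after the draw is not obviously irrelevant.

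The definition also carries over. SAP 3.2, 3.3 and 3.4 reuse the primary modelling framework for secondary, exploratory and subgroup analyses, and 3.3 may apply it to row 1.1 events. The event class therefore has to be stated for each use.

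**Working it through.** **Inputs from the documents.** Margin 0.0015 (SAP 3.1.2). One-sided 2.5% level, 24,000 donations split 1:1 (12,000 per arm), event rate 0.0015 and power above 85% at no difference (SAP 5). Protocol 1.1 gives about 0.15% as the rate of *significant* hypotensive events.

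**Assumed inputs.** The documents do not give the rate of all hypotensive events (0.225% to 0.5% used here) or the share of significant events arising after the procedure (10% to 50% used here). Donations are treated as independent.

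**Formula.** For true rates pC and pE, the chance that the Wald upper limit falls below the margin is

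Φ( [0.0015 − (pE − pC)] / SE − 1.96 ), with SE = √{ [pC(1 − pC) + pE(1 − pE)] / 12,000 }.

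**Step 1: the plan's own figure.** With pC = pE = 0.0015, SE = 0.000500 and 0.0015/SE = 3.00, so power = Φ(1.04) = 85.1%. For 85% power the formula needs 11,954 donations per arm, or 23,908 in total against 24,000 planned. The stated power therefore matches the rate for significant events. The simulated power in SAP Table 1 for true differences of 0.0005 to 0.0015 does not reproduce under independence (at the margin, 2.5% here against 5.7% there), but nothing below depends on those columns.

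**Step 2: post-procedure events dropped, doubling spread evenly.** True rates are 0.0015 and 0.0030, so the true difference equals the margin. Dropping a share f multiplies both rates by (1 − f).

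| Share dropped | pC, pE seen | SE | Chance of declaring non-inferiority |
|---|---|---|---|
| 0% | 0.00150, 0.00300 | 0.000612 | 2.5% |
| 10% | 0.00135, 0.00270 | 0.000580 | 4.4% |
| 20% | 0.00120, 0.00240 | 0.000547 | 7.9% |
| 30% | 0.00105, 0.00210 | 0.000512 | 14.0% |
| 50% | 0.00075, 0.00150 | 0.000433 | 41.0% |

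For the 30% row, (0.0015 − 0.00105)/0.000512 = 0.88, and Φ(0.88 − 1.96) = 14.0%. Exact Poisson enumeration of the same rule gives about 9%, 16% and 44% at 20%, 30% and 50%, against about 3% with nothing dropped.

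**Step 3: the extreme case.** If the whole excess arises after the procedure, a during-only analysis sees 0.0015(1 − f) in both arms. The chance of declaring non-inferiority is then about 92%, 95% and 99% at 20%, 30% and 50%.

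**Step 4: minor events counted, no true difference.**

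| Rate of all hypotensive events | Power |
|---|---|
| 0.15% (significant only) | 85.1% |
| 0.225% | 68.9% |
| 0.3% | 56.5% |
| 0.5% | 37.7% |

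**The case against.** The best defence is that the sentence is loose wording and that the rest of the plan shows what is meant.

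- **On event class this largely succeeds.** A reader might infer that the primary outcome has become any hypotensive event. The documents do not support that. The last paragraph of 3.1.1 names significant rates, the planning rate is the protocol's rate for significant events, and row 1.1 is analysed separately. The SAP shortens to a bare *AE* elsewhere (sections 3.4 and 5). Protocol 9 also requires major changes to the primary endpoint definition to appear in a protocol amendment. What remains is a section that contradicts itself.
- **On timing it succeeds only in part.** No text says that later reactions will be excluded, and SAP 2.2.1 and 2.2.2 point to including them. A reader might argue that the limit must be deliberate because, among endpoint definitions, the protocol speaks of events during the procedure only in the exploratory ones. That inference fails: Protocol 2.1 uses similar wording for significant events in general, with no sign of a narrower window. But nothing in 3.1.1 corrects the limit, so two codings of a late reaction can be defended from the text.
- **On mechanism.** Protocol 2.4 also names extracorporeal volume during the procedure as an influence. It expects saline to keep the end-of-procedure deficit low and calls that deficit an unlikely source of added risk. The same section simulates a top-quartile deficit of 6.6% to 8.4% in the experimental arm against 4.8% to 7.3% in control. This makes late reactions worth counting. It does not show that an excess will arise there.
- **On size.** A reader might quote 92% to 99% as the risk of a false non-inferiority claim. Those figures need the entire doubling to arise after the procedure. At a 30% share, that means late events rising from 0.00045 to 0.00195, a 4.3-fold increase, with no effect during the draw. Nothing in the documents supports that as the expected case.

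**Conclusion.** The point holds as a conflict within the plan, not as a settled change of endpoint. The variable definition in SAP 3.1.1 disagrees with the section's own last paragraph, with the primary endpoint and with the Study Adverse Event and ITT definitions. The timing limit is the weightier half, because it has no correction within the section and its error runs towards declaring safety.

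With an evenly spread doubling, losing 20% to 50% of events would raise the chance of declaring non-inferiority at the margin from 2.5% to between about 8% and 41%. Counting minor events would reduce power from 85% to about 57% or 38% at total rates of 0.3% or 0.5%. All of these figures rest on assumed rates and shares and on independent donations. They show what literal coding could do, not what the trial will do. The sentence should be corrected before the primary analysis is programmed.

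**What to change.** Replace the defining sentence in SAP 3.1.1 with:

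*AE = 1 if at least one significant (IQPP 1.2-1.6) hypotensive AE was reported as associated with the study donation, whether during or after the procedure; otherwise 0.*

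It would also help to state how long after the procedure a reaction can still be attributed to the donation, since SAP 2.2.1 gives no window. Where SAP 3.3 applies the framework to row 1.1 events, name that event class there.

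The cost is one SAP sentence, plus the optional clarifications. The planning rate stays at 0.15%, power stays at 85.1% by the calculation above, and no donations are added. Because the change restores the protocol's endpoint, it does not alter the endpoint definition there.
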